#### 7.5.11 PFS2

PFS2 will be analyzed similarly to PFS:

 Median values based on KM method, along with two-sided 95% CI using Brookmeyer and Crowley method will be calculated. The estimate of standard error will be calculated using the Greenwood formula.

- The estimate of the PFS2 hazard ratio between treatment groups will be calculated using a stratified Cox proportional hazards model, with treatment as the sole covariate. A two-sided 95% CI for the hazard ratio will also be presented
- PFS2 will be graphically displayed along with the median and 95% CI.

A by-subject listing of PFS and PFS2 will be provided

# 7.6 Safety

All figures and summary tables for safety will be produced on the "all treated PD-L1 CPS  $\geq$  20," and "all treated" populations. Safety listings will be done on the all treated populations but will have variables for PD-L1 CPS added to them.

Analyses in this section will be tabulated by treatment group as treated, unless otherwise specified.

#### 7.6.1 Deaths

Deaths will be summarized by treatment group:

- All deaths, reasons for death.
- Deaths within 30 days of last dose received, reasons for death.
- Deaths within 100 days of last dose received, reasons for death.

A by-subject listing of deaths will be provided for the all enrolled subjects population.

#### 7.6.2 Serious Adverse Events

Serious adverse events will be summarized by treatment group:

- Overall summary of SAEs by worst CTC grade (any grade, grade 3-4, grade 5) presented by SOC/PT.
- Overall summary of drug-related SAEs by worst CTC grade (any grade, grade 3-4, grade 5) presented by SOC/PT.

All analyses will be conducted using the 30-day safety window.

A by-subject SAE listing will be provided for the "enrolled subjects" population.

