Either a formalin-fixed, paraffin-embedded (FFPE) tissue block or unstained tumor tissue sections (archival or recent), with an associated pathology report, must be submitted for biomarker evaluation prior to randomization as described in [Section 5.6.3](#). Biopsy should be excisional, incisional, or core needle. Fine needle aspiration is insufficient. Biopsies of bone lesions that do not have a soft tissue component are unacceptable for submission.

- h) **As of Revised Protocol 02, this criterion has been altered and rewritten as criterion 2.1.** *Prior palliative radiotherapy must have been completed at least 8 weeks prior to randomization if radiotherapy was to the head and neck region and 4 weeks prior to randomization if radiotherapy was to other regions.*
- i) All toxicities attributed to prior systemic anti-cancer therapy or surgery other than alopecia and fatigue must have resolved or returned to baseline at least 2 weeks before randomization.
- j) Participants must have a life expectancy of at least 3 months. Any participants whose body weight decreased by > 10% between the screening visit and randomization must be excluded from the study.
- k) **As of Revised Protocol 02, this criterion has been removed because it is already part of criterion c.** *Participants having progression after 2 cycles of induction chemotherapy are excluded.*
- l) Prior radiotherapy must have been completed at least 2 weeks prior to randomization. All toxicities attributed to the radiotherapy must have resolved or returned to baseline prior to treatment.

3. Age and Reproductive Status

- a) Males and Females, ages ≥ 18 years of age
- b) Women of childbearing potential (WOCBP) must have a negative serum or urine pregnancy test (minimum sensitivity 25 IU/L or equivalent units of HCG) within 24 hours prior to the start of study drug.
- c) Women must not be breastfeeding
- d) WOCBP must agree to follow instructions for method(s) of contraception from the time of enrollment for the duration of treatment plus 5 half-lives of nivolumab (half-life up to 25 days) plus 30 days (duration of ovulatory cycle) for a total of 5 months post treatment completion (Arm A).

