6.1.1 Serious Adverse Event Collection and Reporting

Sections 5.6.1 and 5.6.2 in the Investigator Brochure (IB) represent the Reference Safety Information to determine expectedness of serious adverse events for expedited reporting. Following the participant's written consent to participate in the study, all SAEs, whether related or not related to study drug, must be collected, including those thought to be associated with protocol-specified procedures.

All SAEs must be collected that occur during the screening period and within 100 days of discontinuation of dosing. If applicable, SAEs must be collected that relate to any later protocol-specified procedure (eg, a follow-up skin biopsy). For participants randomized/assigned to treatment and never treated with study drug, SAEs should be collected for 30 days from the date of randomization/treatment assignment.

The investigator must report any SAE that occurs after these time periods and that is believed to be related to study drug or protocol-specified procedure.

An SAE report must be completed for any event where doubt exists regarding its seriousness.

If the investigator believes that an SAE is not related to study drug, but is potentially related to the conditions of the study (such as withdrawal of previous therapy or a complication of a study procedure), the relationship must be specified in the narrative section of the SAE Report Form.

SAEs, whether related or not related to study drug, and pregnancies must be reported to BMS (or designee) within 24 hours of awareness of the event.

SAEs must be recorded on the SAE Report Form;

Pregnancies on a Pregnancy Surveillance Form (electronic or paper forms).

The required method for SAE data reporting collection is through the eCRF.

The paper SAE/pregnancy surveillance forms are only intended as a back-up option when the eCRF system is not functioning. When paper forms are used, the original paper forms are to remain on site. In this case, the paper forms are to be transmitted via email or confirmed facsimile (fax) transmission to:

SAE Email Address: Refer to Contact Information list.

SAE Facsimile Number: Refer to Contact Information list.

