8.4.3 Safety Analyses

Safety analyses are restricted to treated participants. Descriptive statistics of safety will be presented using the National Cancer Institute (NCI) Common Terminology Criteria for Adverse Events (CTCAE) version 4.0 by treatment arm. All AEs, drug-related AEs, SAEs and drug-related SAEs will be tabulated using the worst grade per NCI CTCAE v 4.0 criteria by system organ class and preferred term. On-study lab parameters including hematology, coagulation, chemistry, liver function and renal function will be summarized using worse grade per NCI CCAE v 4.0 criteria. These analyses will be performed on both the population of treated participants with PD-L1 expressing tumors and on all treated participants.

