#### • Post baseline period:

- On-treatment AEs will be defined as AEs with an onset date and time on or after the date and time of the first dose of study treatment (or with an onset date on or after the day of first dose of study treatment if time is not collected or is missing). For subjects who are off study treatment, AEs will be included if event occurred within a safety window of 100 days after the last dose of study treatment. No "subtracting rule" will be applied when an AE occurs both pre-treatment and post-treatment with the same preferred term and grade.
- On-treatment evaluations (laboratory tests, pulse oximetry and vital signs) will be defined as evaluations taken after the day (and time, if collected and not missing) of first dose of study treatment. For subjects who are off study treatment, evaluations should be within a safety window of 100 days after the last dose of study treatment.

 Late-emergent drug-related AEs will be defined as drug-related AEs with an onset date greater than 100 days after the last dose of study treatment in subjects who are off study treatment.

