#### 7.6.5 Adverse Events

Adverse events will be summarized by treatment group.

The following analyses will be conducted using the 30 days safety window only:

- Overall summary of any AEs by worst CTC grade (1, 2, 3, 4, 5, not reported, total) presented by SOC/PT.
- Overall summary of any AEs presented by worst CTC grade (any grade, grade 3-4, grade 5) by SOC/PT. This table will be restricted to events with an incidence greater or equal to 5% in any treatment group.
- Overall summary of any non-serious AEs presented by SOC/PT. This table will be restricted to events with an incidence greater or equal to 5% in any treatment group.
- Overall summary of any AEs that required immune modulating medication by worst CTC grade (any grade, grade 3-4, grade 5) presented by SOC/PT.
- Overall summary of drug-related AEs by worst CTC grade (1, 2, 3, 4, 5, not reported, total) presented by SOC/PT.

The following analyses will be conducted using the 30 days safety window and repeated using the 100 days safety window:

• Overall summary of drug-related AEs by worst CTC grade (any grade, grade 3-4, grade 5) presented by SOC/PT.

A by-subject AE listing will be provided. A by-subject listing of any AE requiring immune modulating medications will also be provided.

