#### 7.6.6.1 Incidence of Select AE

Select AEs will be summarized by treatment group for each category/subcategory.

The following analyses will be conducted using the 30-day safety window only:

- Overall summaries of any select AEs by worst CTC grade (any grade, grade 3-4, grade 5) presented by Category or Subcategory/PT.
- Overall summaries of any drug-related select AEs by worst CTC grade (any grade, grade 3-4, grade 5) presented by Category or Subcategory/PT.

- Overall summaries of any serious select AEs by worst CTC grade (any grade, grade 3-4, grade 5) presented by Category or Subcategory /PT.
- Overall summaries of drug-related serious select AEs by worst CTC grade (any grade, grade 3-4, grade 5) presented by Category or Subcategory /PT.
- Overall summaries of any select AEs leading to discontinuation by worst CTC grade (any grade, grade 3-4, grade 5) presented by Category or Subcategory /PT.
- Overall summaries of drug-related select AEs leading to discontinuation by worst CTC grade (any grade, grade 3-4, grade 5) presented by Category or Subcategory /PT.
- Summary of frequency of unique select AEs by Category.

A by-subject select AE listing will be provided.

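### SAEs are collected to 100 days after last dose, but the SAE and serious select-AE tables stop at 30 days, so no by-arm table gives SAE incidence through day 100

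*SAP*

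**What the plan says.** **Collection.** Protocol 6.1.1: "All SAEs must be collected that occur during the screening period and within 100 days of discontinuation of dosing". This applies whether or not the event is thought related to study drug.

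**Default analysis window.** SAP 6.1, for subjects off treatment: "AEs will be included if event occurred within a safety window of 100 days after the last dose of study treatment". SAP 7.1.1 makes on-treatment events the default for AE summary tables, unless a section specifies otherwise.

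**SAE tables.** Protocol 8.4.3 promises that "All AEs, drug-related AEs, SAEs and drug-related SAEs will be tabulated using the worst grade per NCI CTCAE v 4.0 criteria" and names no window. SAP 7.6.2 plans two by-arm tables, all SAEs and drug-related SAEs, and then says "All analyses will be conducted using the 30-day safety window".

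**Serious select AEs.** SAP 7.6.6.1 includes tables of serious and drug-related serious select AEs under the instruction "The following analyses will be conducted using the 30-day safety window only".

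**What does run to day 100.**
- SAP 7.6.5 treats one table of drug-related AEs by worst grade differently: "The following analyses will be conducted using the 30 days safety window and repeated using the 100 days safety window".
- SAP 7.6.1 tabulates deaths overall, to day 30 and to day 100.
- SAP 7.6.7 (immune-mediated AEs, IMAEs) and 7.6.8 (other events of special interest, OEOSI) use 100 days.

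**Listing.** SAP 7.6.2: "A by-subject SAE listing will be provided for the" enrolled-subjects population. No separate window is stated for it.

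**The concern.** The SAE table is the usual headline comparison of serious toxicity. In an open-label trial its all-cause version has a particular value: it does not depend on the investigator's judgement of relatedness. Here that version is cut at day 30, although the data exist to day 100 and the SAP's own default window is 100 days.

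Take a non-fatal serious event on day 60 that is judged unrelated and lies outside the immune-mediated and special-interest term lists. It must be reported and it will appear in a listing, but no by-arm table shows it as a serious event. If such events are not rare, the SAE incidence in the study report is lower than the incidence in the collected data.

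The question matters more when one regimen has a long half-life, because delayed toxicity is then pharmacologically plausible after the 30-day cut.

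**Working it through.** There is no planned figure to reproduce. The check compares windows and then adds simple arithmetic on plausibility and possible size.

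**1. Does any by-arm table give SAE incidence to day 100?**

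| SAP section | Content | Window after last dose | SAE incidence by arm to day 100? |
|---|---|---|---|
| 7.6.2 | all SAEs; drug-related SAEs | 30 days | no |
| 7.6.6.1 | serious and drug-related serious select AEs | 30 days | no |
| 7.6.5 | drug-related AEs by grade | 30 and 100 days | no: related events only, not split by seriousness |
| 7.6.1 | deaths | all, 30 and 100 days | no: fatal outcomes only |
| 7.6.7 | IMAEs | 100 days | no: specified categories; non-endocrine events must also have been treated with immune-modulating medication (7.1.1.3) |
| 7.6.8 | OEOSI | 100 days | no: term list only |
| 7.6.2 | by-subject SAE listing | none stated | no: not a comparison by arm |

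Days collected but outside the SAE tables: 100 − 30 = 70 of 100. This is calendar time, not a share of events.

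**2. Is delayed toxicity plausible in Arm A?** Protocol 3.3.1 bases contraception on "5 half-lives of nivolumab (half-life up to 25 days"), a stated maximum. It agrees with the totals given there:
- women: 5 × 25 + 30 = 155 days; 155 / 30.4375 = 5.1 months (stated: 5)
- men: 5 × 25 + 90 = 215 days; 215 / 30.4375 = 7.1 months (stated: 7)

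Fraction of the last-dose level remaining = 0.5^(days / half-life):

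| Half-life (days) | Day 30 | Day 100 |
|---|---|---|
| 25 (stated maximum) | 0.5^1.2 = 44% | 0.5^4 = 6% |
| 20 (assumed) | 35% | 3% |
| 15 (assumed) | 25% | 1% |

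So 25–44% remains at day 30 for half-lives of 15–25 days. The documents give no half-life for ipilimumab.

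**3. What about Arm B?** For women, Protocol 3.3.1 adds five chemotherapy half-lives to 30 days and still arrives at 30 days, which treats chemotherapy washout as close to zero. The same clause gives way to local labels where these specify longer. It also concerns chemotherapy: cetuximab maintenance continues after at most six chemotherapy cycles, so for participants on maintenance the last dose that starts the window is cetuximab. The documents give no cetuximab half-life.

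**4. How far could the comparison move?** Let a and b be the shares of subjects in Arms A and B whose only SAE falls on days 31–100. Moving from 30 to 100 days changes the A − B difference in subjects with an SAE by a − b. The documents give neither share, so assume 0–10% for each. With about 930 / 2 = 465 per arm (randomized, as an approximation to treated), 10% is about 46 subjects.

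| a | b | Change in A − B |
|---|---|---|
| 10% | 0% | +10 points |
| 5% | 2% | +3 points |
| 5% | 5% | 0 |
| 2% | 5% | −3 points |
| 0% | 10% | −10 points |

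The range is symmetric about zero because nothing in the documents fixes the sign.

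**The case against.** **The 30-day window is a deliberate choice, not a contradiction.** The 100-day definition is only a default, and 7.6.2 overrides it openly. So do the sections on discontinuations, dose modification, select AEs and laboratory tests. SAP 7.1.1 itself expects 30 or 100 days depending on the analysis. The scheme is coherent: 30 days for general toxicity, 100 days for immune-mediated events. This stands, and the point is not an inconsistency claim. It is that a useful comparison is missing.

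**Late serious toxicity is largely covered elsewhere.** Deaths to day 100 are tabulated by arm, and every drug-related SAE to day 100 is contained in the 7.6.5 repeat by grade. This narrows the gap but does not close it. Grade is not seriousness, and unrelated non-fatal SAEs outside the term lists are still missing.

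**A 100-day all-cause table is harder to read.** With planned median OS of 10.8 to 13 months in all randomized subjects, late SAEs will include effects of disease and next-line treatment, and the safety sections state no cut at subsequent therapy. This is true, and it is why the 30-day tables should stay. The SAP has already accepted the same mixing for deaths and drug-related AEs.

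**A stronger reading to resist.** A reader might infer that the 30-day cut mainly flatters the immunotherapy arm. The documents do not support that. Residual drug is not an event rate, 25 days is a maximum, and no SAE rates are given for days 31–100. Low residual exposure is not shown for cetuximab. The opposite direction is possible too: Arm A may be treated beyond progression while Arm B stops at it, so late Arm B SAEs could include next-line toxicity.

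**Conclusion.** The gap is real and modest. SAEs are collected, and on-treatment AEs defined, to day 100, yet no planned by-arm table gives all-cause or drug-related SAE incidence beyond day 30. Delayed SAEs may therefore be under-counted. In Arm A this is plausible on the protocol's own half-life (up to about 44% of nivolumab remaining at day 30; 25–44% for assumed half-lives of 15–25 days). The size and direction of any between-arm effect cannot be determined: the ±10-point range above rests wholly on assumed late-only SAE shares of 0–10% per arm. The primary endpoints and error control are not affected. This is an inexpensive improvement to the safety reporting and does not depend on which arm has more late events.

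**What to change.** In SAP 7.6.2, keep the 30-day tables of all SAEs and drug-related SAEs and repeat both with the 100-day window, using the wording of SAP 7.6.5 as the model. Do the same for the serious and drug-related serious select-AE tables in SAP 7.6.6.1. Show the two windows side by side, with a note that events after day 30 may reflect disease progression or subsequent therapy.

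**Cost.** No new data are needed. Four tables are repeated, each on the two safety populations of SAP 7.6 (all treated, and treated with PD-L1 CPS ≥ 20): 4 × 2 = 8 runs, plus the endocrine subcategory repeats. The one interpretive cost is the mixing of late events with disease and next-line effects, which the paired display lets the reader judge.

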# 7.6.3 Adverse Events Leading to Discontinuation of Study Therapy

AEs leading to discontinuation will be summarized by treatment group:

- Overall summary of AEs leading to discontinuation by worst CTC grade (any grade, grade 3-4, grade 5) presented by SOC/PT.
- Overall summary of drug-related AEs leading to discontinuation by worst CTC grade (any grade, grade 3-4, grade 5) presented by SOC/PT.

The analyses will be conducted using the 30-day safety window.

A by-subject AEs leading to discontinuation listing will be provided.

#### 7.6.4 Adverse Events Leading to Dose Modification

AEs leading to dose delay/reduction will be summarized by treatment group:

- Overall summary of AEs leading to dose delay/reduction by worst CTC grade (any grade, grade 3-4, grade 5) presented by SOC/PT.
- Overall summary of related AEs leading to dose delay/reduction by worst CTC grade (any grade, grade 3-4, grade 5) presented by SOC/PT.

The analysis will be conducted using the 30-day safety window.

A by-subject AEs leading to dose delay/reduction listing will be provided.

#### 7.6.5 Adverse Events

Adverse events will be summarized by treatment group.

The following analyses will be conducted using the 30 days safety window only:

- Overall summary of any AEs by worst CTC grade (1, 2, 3, 4, 5, not reported, total) presented by SOC/PT.
- Overall summary of any AEs presented by worst CTC grade (any grade, grade 3-4, grade 5) by SOC/PT. This table will be restricted to events with an incidence greater or equal to 5% in any treatment group.
- Overall summary of any non-serious AEs presented by SOC/PT. This table will be restricted to events with an incidence greater or equal to 5% in any treatment group.
- Overall summary of any AEs that required immune modulating medication by worst CTC grade (any grade, grade 3-4, grade 5) presented by SOC/PT.
- Overall summary of drug-related AEs by worst CTC grade (1, 2, 3, 4, 5, not reported, total) presented by SOC/PT.

The following analyses will be conducted using the 30 days safety window and repeated using the 100 days safety window:

• Overall summary of drug-related AEs by worst CTC grade (any grade, grade 3-4, grade 5) presented by SOC/PT.

A by-subject AE listing will be provided. A by-subject listing of any AE requiring immune modulating medications will also be provided.

#### 7.6.6 Select Adverse Events (EU Submission)

Unless otherwise specified, analyses will be performed by select AE category. Analyses will also be repeated by subcategory of endocrine events.

#### 7.6.6.1 Incidence of Select AE

Select AEs will be summarized by treatment group for each category/subcategory.

The following analyses will be conducted using the 30-day safety window only:

- Overall summaries of any select AEs by worst CTC grade (any grade, grade 3-4, grade 5) presented by Category or Subcategory/PT.
- Overall summaries of any drug-related select AEs by worst CTC grade (any grade, grade 3-4, grade 5) presented by Category or Subcategory/PT.

- Overall summaries of any serious select AEs by worst CTC grade (any grade, grade 3-4, grade 5) presented by Category or Subcategory /PT.
- Overall summaries of drug-related serious select AEs by worst CTC grade (any grade, grade 3-4, grade 5) presented by Category or Subcategory /PT.
- Overall summaries of any select AEs leading to discontinuation by worst CTC grade (any grade, grade 3-4, grade 5) presented by Category or Subcategory /PT.
- Overall summaries of drug-related select AEs leading to discontinuation by worst CTC grade (any grade, grade 3-4, grade 5) presented by Category or Subcategory /PT.
- Summary of frequency of unique select AEs by Category.

A by-subject select AE listing will be provided.

#### 7.6.6.2 Time-to Onset of Select AE

Time-to onset of drug-related select AEs (any grade, grade 3-5) will be summarized for each category/subcategory by treatment group.

Time-to onset analyses are restricted to treated subjects who experienced at least one drug-related select AE in the category/subcategory. The analyses will be conducted using the 30-day safety window.

Additional details regarding the time-to onset definition are described in time-to onset definition subsection of APPENDIX 1.

#### 7.6.6.3 Time-to Resolution of Select AE

Time-to resolution of the following specific events will be summarized separately for each category/subcategory.

- Time-to resolution of drug-related select AE (any grade, grade 3-5) by treatment group
- Time-to resolution of drug-related select AE (any grade, grade 3-5) where immune modulating medication was initiated, by treatment group

Time-to resolution analyses are restricted to treated subjects who experienced the specific events. Time-to resolution where immune modulating medication was initiated analyses are restricted to treated subjects who experienced the specific events and who received immune modulating medication during the longest select AE.

The analyses will be conducted using the 30-day safety window.

The following summary statistics will be reported: percentage of subjects with resolution of the longest select AE, median time-to resolution along with 95% CI (derived from Kaplan-Meier estimation) and ranges.

See time-to resolution definition subsection of APPENDIX 1 for additional details.

